4.5 Immunogenicity

Not applicable.

4.6 Safety Analyses

The domain “Safety” covers exposure, treatment compliance, AEs, clinical laboratory, vital signs, ECG, ECHO, ophthalmologic examinations, Knee/Wrist MRI/X-ray, performance status, **CCI** tests.

Safety data will be presented for all participants in the safety analysis set.

All planned data, including off-treatment data for participants who entered the long-term safety follow-up (participants < 5 years of age after 25 cycles of treatment or when they terminate treatment with selumetinib), will be presented in the listings for those assessments specified in the CSP Table 3.

Off-treatment data for participants who entered the long-term safety follow-up (participants < 5 years of age after 25 cycles of treatment or when they terminate treatment with selumetinib) will be presented separately in the summary tables and figures (if not otherwise specified) for those assessments specified in the CSP Table 3.

Off-treatment data will be included up until the first visit after the participant is \geq 5 years of age or they commence an alternative systemic NF1-PN targeted treatment, whichever is earlier.

4.6.1 Exposure and treatment compliance

4.6.1.1 Definitions and Derivations

Duration of exposure will be defined as follows:

- Duration of exposure = last dose date where dose > 0 mg – first dose date + 1 (if last dose date is missing the earliest date between DCO, date of death and treatment discontinuation date will be used).
- Actual duration of exposure = duration of exposure – total duration of dose interruptions, where duration of exposure will be calculated as above, and a dose interruption is defined as any days with dose = 0 mg and half days if planned frequency is twice per day, but actual frequency is once daily only

This calculation will use the individual start and stop dates and the study intervention dosing frequency on the EX form of the CRF, which will account for any dose interruptions. The actual duration of exposure calculation makes no adjustment for any dose reductions that may have occurred.

Participants who permanently discontinue during a dose interruption

If a participant permanently discontinues study intervention during a dose interruption, then the date of last administration of study medication will be used in the calculation of exposure. In this case, the interruption would not be included in the summary tables, but it will be included in the listings.

Relative dose intensity

RDI is the percentage of the actual dose delivered relative to the intended dose through to study intervention discontinuation. RDI will be defined as follows:

- $RDI = 100\% * d/D$, where d is the actual cumulative dose delivered up to the actual last day of dosing and D is the intended cumulative dose up to the day of treatment discontinuation or actual last day of dosing. D is the total dose that would be delivered if the participant received the planned dose as per the CRF.

Intended cumulative dose is calculated by summing all the individual doses that should have been taken up to and including the last day of treatment according to the protocol planned dose and schedule. This is defined as follows:

Integer part (rounded up) of $[(\min(\text{date of last dose date where dose} > 0, \text{date of death, date of DCO}) - \text{first dose date} + 1) \times \text{intended dose according to the protocol}] / 0.5$
The intended dose of selumetinib is $\text{[REDACTED]} \text{ mg/m}^2$ twice daily.

Actual cumulative dose will be calculated by summing all the individual doses the participant actually took up to and including the last day of treatment. This is defined by:

Sum of $[((\text{end date of study drug administration} - \text{start date of study drug administration} + 1) \times \text{dose}) / 0.5]$ for each cycle of drug administration recorded on the study drug exposure form up to the minimum of $[\text{date of last dose date where dose} > 0, \text{date of death, date of DCO}]$.

Treatment compliance

Treatment compliance is the percentage of the actual cumulative dose taken relative to the intended cumulative dose according to the protocol, including the protocol-allowable dose reductions / dose interruptions up to and including the last day of treatment.

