a. After 25 cycles (or discontinuation of selumetinib) participants who are aged < 5 years will enter a long term safety follow-up and assessments will be performed as per Table 3. After 25 cycles of treatment if participants are > 5 years of age and unable to access commercial supply and are still receiving clinical benefit participants may be able to remain on treatment in the study. Assessments will revert to standard of care at the particular site. There will be no more data collection except SAE, overdose and pregnancy reporting. All SAEs, overdoses and pregnancies will be reported until 30 days after last dose.

b. Once participants attain a BSA between 1.10 and 1.29 m^2 they will be encouraged to completely transition to the capsule formulation, if feasible, although all participants must remain on the granule formulation until after they have completed their third cycle of treatment.

c. An EoT visit will be performed for participants who permanently discontinue study intervention for any reason (except for death, lost to follow-up, or withdrawal of consent). The EoT visit should be performed as soon as possible after the end of treatment.

d. Calculation of BSA should be done at the specified time points but since BSA determines the dose of selumetinib it should also be calculated more frequently, as appropriate, depending on the age and growth rate of the child.

e. Assessment of baseline disease characteristics includes documenting location of the target and non-target PN (if applicable), any PN-related symptoms and results of any previous genetic testing for NF1. (Participants recruited under CSP Version 1.0 will have this data entered in the EDC if available retrospectively.)

- f If clinical safety laboratory assessments, urinalysis and performance status have been done within 14 days of starting study intervention they do not need to be repeated on C1D1 if the participant's condition has not changed. If laboratory procedures were performed for alternate reasons prior to signing consent (but within the 28 day screening window), these can be used for screening purposes with consent of the legally authorised representative (parent or guardian) of the participant.

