# 8.4.1 Time Period and Frequency for Collecting AE and SAE Information

Adverse events will be collected from the time of signature of the ICF until 30 days after the last dose of selumetinib or 25 cycles of treatment, whichever is earlier. For participants taking part in the long term safety follow-up (participants < 5 years of age), after 25 cycles of treatment or end of treatment, adverse events causally related to selumetinib will be collected until they complete the study in accordance with Table 3. No AEs will be collected for participants who are > 5 years of age who remain in the study after 25 cycles of treatment.

SAEs will be collected from time of signing the ICF throughout a subject's participation in the study.

If the Investigator becomes aware of an SAE with a suspected causal relationship to the IMP that occurs after the end of the clinical study in a participant treated by him or her, the Investigator shall, without undue delay, report the SAE to the Sponsor.

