3.1 Timing of Analyses

There are 3 planned DCOs for this study.

1 Pharmacokinetic, dose-finding, and primary safety analysis (DCO1): DCO1 will occur after all participants have had the opportunity to complete 3 cycles of treatment. This primary analysis will confirm the recommended granule formulation dose schema and assess the PK, safety/tolerability, and palatability. The timing of DCO1 may be different for the Global Cohorts (Cohorts 1 and 2) from the Japan Cohort based on their date of Last Subject In.

2 Safety and efficacy of the granule formulation (DCO2):

DCO2 will occur after all participants in the study (Global and Japan Cohorts) have had the opportunity to complete 25 cycles (or terminated selumetinib); this analysis will provide additional PK and safety/tolerability data, as well as palatability and efficacy data.

3 Long term safety follow-up for participants until they reach the age of 5 years or commence an alternative systemic NF1-PN treatment, whichever is the earlier (Final analysis and DCO3):

DCO3 and final analysis will occur when all participants in the study (Global and Japan Cohorts) have had the opportunity to complete their last assessment in the study, including the safety follow-up for participants aged < 5 years. All of the safety/tolerability analyses will be updated with the data captured after DCO2 (safety of the granule formulation).

The different analyses planned for the DCOs are provided in [Table 1](#).

Table 1 Summary of Outcome Variables and Timing of Analyses

Outcome variable	Timing of analyses
Study population/demographic data	
Outcome variable	Timing of analyses
Disposition	DCO1, DCO2, and DCO3

Analysis sets	DCO1
Demographic characteristics	DCO1
Baseline and disease characteristics	DCO1
Important protocol deviations	DCO1, DCO2, and DCO3
Medical history	DCO1
Prior and concomitant medication	DCO1, DCO2, and DCO3
Efficacy data	
ORR CCI	DCO2
Clinical outcome assessment data	
Parent-reported palatability	DCO1 and DCO2
CCI	DCO2
CCI	DCO2
CCI	DCO2
CCI	DCO2
Outcome Variable	Timing of analyses
CCI	DCO2
CCI	DCO2
Safety Data	
Exposure and treatment compliance	DCO1, DCO2, and DCO3
Adverse events	DCO1, DCO2, and DCO3
Laboratory measurements	DCO1, DCO2, and DCO3
Vital signs (including height, weight, and BSA)	DCO1, DCO2, and DCO3
ECG and ECHO	DCO1, DCO2, and DCO3
Ophthalmologic assessments	DCO1, DCO2, and DCO3
Knee (or wrist) MRI/X-ray	DCO1, DCO2, and DCO3
Performance status	DCO1, DCO2, and DCO3

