3.3.3 On-Treatment MRI

On-treatment MRI data will be defined as MRI data after the date of first dose of study intervention until the study intervention discontinuation date, DCO, or last day of Cycle 25, whichever occurs first.

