4.2 Endpoint Analyses

This section covers details related to the endpoint analyses such as primary, secondary, and other endpoints including sensitivity and supportive analyses.

The CCI [REDACTED] and CCI [REDACTED] analyses will not form part of the clinical study report and will not be handled by the statistical and programming vendor. The CCI [REDACTED] and CCI [REDACTED] analyses will be analysed and presented separately from the main clinical study report. Thus, they are outside the scope of this SAP.

Statistical category	Endpoint	Population	Population level summary (analysis)	Details in section
To determine the PK of selumetinib after administration of the selumetinib granule formulation				
Primary	Selumetinib AUC0-12 derived after single dose administration	PK	Descriptive statistics	4.4
To assess the safety and tolerability of the selumetinib granule formulation				
Primary	AEs, AESIs and SAEs. Duration of exposure and treatment compliance percentage. Absolute values and changes from baseline in Laboratory assessments. Vital signs, ECG, ECHO, ophthalmologic assessment, Knee (or wrist) MRI/X ray, and performance status.	Safety	Descriptive statistics	4.6
To assess the palatability of the selumetinib granule formulation				
Secondary	Palatability will be assessed using the parent-reported observer palatability assessment.	Safety	Descriptive statistics	4.2.3
To further assess the PK of selumetinib and N-desmethyl selumetinib metabolite after administration of the selumetinib granule formulation				

Statistical category	Endpoint	Population	Population level summary (analysis)	Details in section
Secondary	Single and multiple dose plasma concentrations and PK parameters of selumetinib and N-desmethyl selumetinib (see Section 4.4 for list of parameters).	PK	Descriptive statistics	4.4
To evaluate the efficacy of the selumetinib granule formulation by assessment of ORR as determined by ICR per REiNS criteria				
Secondary	ORR Safety ORR estimate and	4.2.5	two-sided 95% CI based on the exact CCI	

To evaluate the efficacy of the selumetinib granule formulation by assessment of CCI [REDACTED] and CCI as determined by ICR per REiNS criteria				
Exploratory	CCI [REDACTED]	Participants who have a CCI [REDACTED] in safety	CCI [REDACTED] CCI [REDACTED] CCI [REDACTED] CCI [REDACTED]	4.2.6
Exploratory	CCI [REDACTED]	Safety	CCI [REDACTED] [REDACTED]	4.2.7
Exploratory	CCI [REDACTED]	Safety	CCI [REDACTED] CCI [REDACTED]	4.2.8

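### SAP 4.6.1.1 sets no Cycle 25 limit on exposure, so at DCO2 it may be run to the data cut-off for children over 5 whose dosing is no longer recorded

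*SAP*

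**What the plan says.** **Exposure rule (SAP 4.6.1.1).** Duration runs from first dose to last non-zero dose, and "if last dose date is missing the earliest date between DCO, date of death and treatment discontinuation date will be used". Actual duration subtracts dose interruptions: "This calculation will use the individual start and stop dates and the study intervention dosing frequency on the EX form of the CRF". Intended cumulative dose runs to the earliest of last non-zero dose, death and DCO. Actual cumulative dose sums the administrations recorded on the exposure form. Cycle 25 is not mentioned.

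**After Cycle 25 (Protocol 1.3, Table 2, footnote a).** Children over 5 who cannot get commercial supply and "are still receiving clinical benefit participants may be able to remain on treatment in the study". For them, "There will be no more data collection except SAE, overdose and pregnancy reporting". Protocol 8.4.1 adds: "No AEs will be collected for participants who are > 5 years of age who remain in the study after 25 cycles of treatment". SAP 4.6.2.1 repeats this. SAEs are still reported. Protocol 4.1.2 treats children aged 5 or over at the end of 25 cycles as complete for analysis.

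**Timing.** Under SAP 3.1, DCO2 waits until every participant could have finished 25 cycles or has stopped. SAP 4 uses all available data at DCO1 and DCO2.

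**Contrast.** SAP 3.3.3 counts MRI as on-treatment only "until the study intervention discontinuation date, DCO, or last day of Cycle 25, whichever occurs first".

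**Status.** The primary safety row of SAP 4.2 includes "Duration of exposure and treatment compliance percentage".

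**The concern.** The DCO fallback suits DCO1, when children still on treatment are generally still within the period in which dosing is recorded. The same text governs DCO2, and there it does not fit. An early entrant who continues on study supply has passed Cycle 25, is still taking drug, and no longer supplies dosing data. If no last dose date is on file, the DCO is used. Actual duration then subtracts nothing for that stretch, because no interruption could have been recorded.

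Three summaries are at stake: exposure, RDI and compliance, all presented by cohort. Their tables would mix time with full dosing and AE collection and time with neither. A reader would naturally set the AE counts beside that longer exposure.

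**Working it through.** **1. Schedule.** Cycles last 28 days (Protocol Table 2). Cycle 25 Day 1 is study day 24 × 28 + 1 = 673, in week 672/7 + 1 = 97, which matches Table 2. Cycle 25 ends on day 25 × 28 = 700.

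**2. Is an open last dose date likely?** The last scheduled drug return and compliance check in Table 2 is at Cycle 25 Day 1. The end-of-treatment visit is only for those who permanently discontinue. So no scheduled event gives a continuing child a last dose date. The documents do not show how the exposure form is closed, so this is the natural result and not a certain one.

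**3. Who can be affected?** 700 days is 700/365.25 = 1.92 years. A child must be at least 5 − 1.92 = 3.08 years old at first dose to be 5 when Cycle 25 ends. That covers all of Cohort 1 and, if ages are uniform over 1 to 4 years (an assumption), (4 − 3.08)/3 = 31% of Cohort 2. Japan Cohort children of those ages are included too. Only those who stay on study supply count.

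**4. Excess duration.** Let u be the days from a child's first dose to the last participant's first dose. Take DCO2 as the last first dose + 700 days. Imputed duration is then 700 + u, and the excess is u. With uniform accrual over A days, the mean excess among continuing children is A/2. If a share p continues, regardless of entry date, the overall mean rises by p × A/2 on a base of 700. Neither A nor p is stated, so both are assumed (month = 30.4375 days).

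| Accrual | First child in (700 + A) | Mean, continuing (700 + A/2) | Excess, continuing | Overall excess, p = 25% | Overall excess, p = 50% |
|---|---|---|---|---|---|
| 6 months | 883 days | 791 days | 13.0% | 3.3% | 6.5% |
| 12 months | 1065 days | 883 days | 26.1% | 6.5% | 13.0% |
| 18 months | 1248 days | 974 days | 39.1% | 9.8% | 19.6% |
| 24 months | 1430 days | 1065 days | 52.2% | 13.0% | 26.1% |

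The documents give only an outer limit on accrual: 998 days from the original protocol (5 August 2021) to the SAP revision of 29 April 2024, by which time all subjects were included (SAP 4.3.3).

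**5. RDI and compliance.** Suppose the DCO replaces the missing last dose date in the intended dose, while recorded administrations stop at day 700. A fully compliant child on a constant dose then has RDI = 700/(700 + u). For the first child in, this is 79.3%, 65.7%, 56.1% or 48.9% at 6, 12, 18 or 24 months' accrual. The mean over continuing children is 88.9%, 80.5%, 73.9% or 68.5%. Compliance compares intended and actual dose in the same way, so it could fall too. If programmers instead extend the open dosing record to the DCO, RDI stays near 100%, but over time with no records. The SAP does not say which applies.

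**6. Children under 5.** They may also continue after Cycle 25. Protocol Table 3 keeps their dispensing and compliance checks, so dosing is still followed. But Protocol 8.4.1 then collects only causally related AEs and SAEs. Their exposure also outruns full AE collection.

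**The case against.** The strongest reply is that the fallback acts only when the last dose date is missing. Dosing comes from start and stop dates on the exposure form, collection ends at Cycle 25, and the protocol calls these children complete at that point. If sites enter a stop date then, exposure ends there and nothing is inflated. This stands as a condition on the finding. Neither document gives that instruction, so the derivation is at best undetermined.

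The added time is also real time on drug, with SAEs and overdoses still captured. That stands. The excess is relative to the dosing records and the non-serious AE data.

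A reader might infer that the safety profile will look better per unit of exposure. The documents do not support this. SAP 4.6.2.2 reports numbers and percentages of participants and plans no exposure-adjusted rate. The possible RDI effect points the other way, making delivery of treatment look worse.

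Endpoint status is also open to challenge. Protocol Table 5 does not list exposure or compliance among the primary safety endpoints, and Protocol 9.4.5 places exposure under other analyses. Only SAP 4.2 lists them as primary.

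Finally, a cap on children aged 5 or over alone would hold Cohort 1 to 700 days while continuing younger children accrued to DCO2. That is right, so any cap should cover everyone.

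**Conclusion.** The concern holds, conditionally. As written, SAP 4.6.1.1 lets unrecorded time after Cycle 25 enter duration and actual duration at DCO2. It may also set an intended dose running to the DCO against an actual dose built only from records. For each continuing child the excess is the gap between that child's Cycle 25 and DCO2. The sizes in the table rest on assumed uniform accrual, an assumed share continuing, and an exposure form left open at Cycle 25.

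Two stronger readings should be avoided. First, 13% to 52% is not the inflation of the whole exposure table. It applies only to children who continue, and footnote a restricts these to children without commercial supply who still benefit. Secondly, the problem does not carry into DCO3 for children aged 5 or over after 25 cycles: SAP 4 limits DCO3 to participants under 5 after 25 cycles or at discontinuation. What remains affects the exposure, RDI and compliance summaries and how AE counts are read beside them.

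**What to change.** In SAP 4.6.1.1, for the DCO2 tables, end duration, actual duration, intended and actual cumulative dose, RDI and compliance at the earliest of last dose, death, discontinuation, DCO and the last day of Cycle 25. Apply this to all participants, matching SAP 3.3.3.

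Report time on selumetinib after Cycle 25 on a separate line. Read it only with the data still collected then: SAEs for children over 5, and SAEs plus causally related AEs for children under 5 in follow-up. No DCO3 change is needed for children aged 5 or over.

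The cost is a sentence or two in the SAP and one derived variable, with no change to data collection or conduct. The downside is that the main table shows a shorter exposure.

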# Capsule Dose Schema for Selumetinib 25 mg/m^2 bid

bid, twice daily; BSA, body surface area.

Granules from the sprinkle capsule should be mixed with a dosing vehicle prior to administration. Detailed instructions will be provided in the IMP handling instruction document or an equivalent document.

The time and content of meals on intensive PK sampling days (Cycle 1 Day 1, Cycle 2 Day 1 and, should the participant transition to capsule formulation, capsule dosing Day 7) should be recorded in source data.

Selumetinib granules are administered twice a day, approximately 12 hours apart. For participants aged  $\geq 1$  to < 4 years selumetinib granules can be taken without regard to food.

For participants aged  $\geq$  4 to < 7 years, on intensive PK sampling days (Cycle 1, Day 1 and Cycle 2, Day 1), selumetinib granules must be taken on an empty stomach (no food or drink other than water for 2 hours before and one hour after dosing, with the exception of vehicle and water to cleanse the palate). On other study treatment days selumetinib may be taken without regard to food.

Where capsules are taken, selumetinib capsules should be swallowed whole with a glassful of water twice a day, approximately 12 hours apart, on an empty stomach (no food or drink other than water for 2 hours prior to dosing and one hour after dosing).

If a dose of selumetinib is missed, it should only be taken if it is more than 6 hours until the next scheduled dose. Do not take an additional dose if vomiting occurs after selumetinib administration but continue with the next scheduled dose.

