# 6.4 Study Intervention Compliance

When participants are dosed at the site (eg, PK days), they will receive study intervention directly from the investigator or designee, under medical supervision. The date, and time if applicable, of dose administered in the clinic will be recorded in the source documents and recorded in the eCRF. The dose of study intervention and study participant identification will be confirmed at the time of dosing by a member of the study site staff other than the person administering the study intervention.

Parents/guardians of the participant will complete a daily drug diary to record the dates and times on which selumetinib is taken.

When participants (self/parent/guardian) administer study intervention at home, compliance with study intervention will be assessed at each visit. Compliance will be assessed by counting returned sprinkle capsules or capsules and reviewing the Drug Diary at each site visit and documenting in the source documents and eCRF. Deviation(s) from the prescribed dosage regimen should be recorded in the eCRF.

A record of the number of selumetinib sprinkle capsules or capsules dispensed to and taken by each participant must be maintained and reconciled with study intervention and compliance records. Intervention start and stop dates, including dates for intervention delays and/or dose reductions will also be recorded in the eCRF.

The Investigational Product Storage Manager is responsible for managing the study intervention from receipt by the study site until the destruction or return of all unused study intervention.

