4.6.1.2 Presentation

Duration of exposure, actual duration of exposure, RDI, and treatment compliance will be summarised using descriptive statistics for continuous data and listed. Counts and percentages for the number of planned starting dose received, dose interruptions, reasons

for dose interruptions, dose reductions, reason for dose reductions, dose modifications (ie, dose interruption and/or dose reduction), and treatment compliance thresholds will be provided.

Treatment compliance percentage will be summarised as a continuous variable using descriptive statistics and by counts and percentages using the following categories:

CCI

CCI

CCI

Exposure and treatment compliance data will be presented by cohort and total.

Exposure data will be listed, including the date of first exposure to treatment, duration (intended) of exposure (days), actual duration of exposure (days), RDI, treatment compliance, and transition to capsule formulation.

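### The SAP's actual-dose formula assumes two doses on every recorded day, so a once-daily period lowers actual duration of exposure but not relative dose intensity

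*SAP*

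**What the plan says.** All of the following is in SAP 4.6.1.1 unless stated.

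- **Actual cumulative dose (d).** In words, "Actual cumulative dose will be calculated by summing all the individual doses the participant actually took". The formula sums (end date − start date + 1) × dose / 0.5 "for each cycle of drug administration recorded on the study drug exposure form up to the minimum of" three dates: last dose above zero, death and data cut-off.
- **Intended cumulative dose (D).** The formula is days from first dose to the earliest of the same three dates, × intended dose / 0.5, rounded up. The text also describes D as the planned dose recorded on the CRF, and a separate sentence gives the intended dose as a mg/m² amount twice daily (value redacted). RDI is 100% × d / D.
- **Actual duration of exposure.** Interruptions are subtracted, including "half days if planned frequency is twice per day, but actual frequency is once daily only". The source named is "the study intervention dosing frequency on the EX form of the CRF".
- **Compliance.** "Treatment compliance is the percentage of the actual cumulative dose taken relative to the intended cumulative dose according to the protocol", allowing for reductions and interruptions that the protocol permits. Among the counts and percentages in SAP 4.6.1.2, "treatment compliance thresholds will be provided".

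In the protocol, section 6.1.1 says "If a dose of selumetinib is missed, it should only be taken if it is more than 6 hours" until the next one is due, so some missed doses are not made up. It also schedules a single dose on Cycle 1 Day 1. Section 6.4 adds: "Deviation(s) from the prescribed dosage regimen should be recorded in the eCRF".

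**The concern.** The words and the formula for d agree only while every recorded day has two doses. For a record with once-daily frequency the words give one dose per day and the formula gives two. The SAP foresees such records, since it has a rule for them in actual duration, but that rule is not carried into d.

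Two measures in one exposure listing could then contradict each other: actual duration falls and RDI stays at 100%. The error runs in one direction. For once-daily periods it can only make dose delivery look better than it was.

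Treatment compliance is defined on the same term, and no other formula for that term is given. It appears in the primary safety row of the SAP 4.2 endpoint table and is reported at all three data cut-offs (SAP Table 1).

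**Working it through.** The documents state no RDI or cumulative dose, so there is no figure to reproduce. The check applies the SAP formulas to simple dosing records.

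**Inputs.** N = days on treatment: 84 for 3 cycles and 700 for 25 cycles of 28 days. k = days with once-daily frequency on the EX form; this is an assumption, as the documents give no number. x = mg per administration; it cancels.

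**Control, all twice daily.** 28 days at an illustrative 30 mg: by formula 28 × 30 / 0.5 = 1680 mg; doses taken 28 × 30 × 2 = 1680 mg. So / 0.5 is a fixed two administrations per day.

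**Once-daily period.** For k days at x mg, the formula gives k·x / 0.5 = 2kx; the dose taken is kx. The ratio is exactly 2, whatever the mg value.

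**RDI.**
- By formula: d = D = N·x / 0.5, so RDI = 100% for any k.
- True, with Cycle 1 Day 1 counted as one dose in both sums: (2N − 1 − k) / (2N − 1).
- SAP actual duration: N − k/2.

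| N | k | RDI by formula | True RDI | SAP actual duration |
|---|---|---|---|---|
| 84 | 7 | 100% | 160/167 = 95.8% | 80.5 days (95.8% of 84) |
| 700 | 7 | 100% | 1392/1399 = 99.5% | 696.5 days (99.5% of 700) |

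The SAP's own actual duration already gives the right proportion from the same records.

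**Days needed for a 5-point error** (ignoring the Cycle 1 Day 1 adjustment): 0.05 × 2N = 8.4, so 9 once-daily days in 84; 70 in 700.

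**Cycle 1 Day 1.** As written, d and D both count two doses on that day, so the error cancels in RDI, although cumulative dose is one dose too high. If only d is corrected, a fully adherent child scores (2N − 1)/(2N): 167/168 = 99.4% at 84 days and 1399/1400 = 99.93% at 700 days. Both sums must change together.

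**The case against.** The strongest reply is about scale. No regimen in the protocol is sustained once-daily dosing: the legible dose-reduction tables keep a morning and an evening dose, and the only scheduled one-dose day cancels in RDI. What remains is missed doses, and the documents do not show how these are entered on the EX form. A missed dose noted only as a deviation would change neither actual duration nor RDI. Interruptions and reductions are tabulated separately, and the protocol's primary safety endpoints (Table 5) name neither RDI nor compliance. All of this stands, and it limits the size. It does not reconcile the formula with its own definition for records that the SAP expects and handles elsewhere.

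A reader might infer more from the same section. The documents do not support these stronger readings:

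- **Two live end dates for D.** The RDI text mentions treatment discontinuation as well as last day of dosing. But the D formula carries one end date, and the paragraph on discontinuation during an interruption also points to the last administration. This is loose wording, not a second rule.
- **A flat mg/m² denominator under which an adherent child need not score 100%.** D is also described as the planned dose per CRF, and the protocol uses 25 mg/m² as a label for its banded mg capsule schema (Table 8 title, Table 11 footnote). The sentence can be read as a label.
- **Misstated dose when morning and evening doses differ.** This depends on how the form holds the dose, and the form is not shown.
- **Any child on half the daily dose is reported at full intensity.** A child reduced to half the dose twice daily is counted correctly. Only a shortfall in frequency is missed.

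**Conclusion.** The point holds in a narrow form. For an EX record with once-daily frequency, the SAP's formula counts twice the dose taken, leaves RDI unchanged while actual duration falls, and contradicts the definition it is meant to implement. Compliance shares the fault as far as it is computed from this formula.

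The size depends on how many once-daily days are recorded, which is unknown. A week of them costs about 4 points of RDI at 84 days and half a point at 700, so the effect is most visible at the first data cut-off. The figures assume one dose value per administration on each record and no other shortfall. RDI and compliance are descriptive; the primary PK analysis and ORR do not use them. The change is worth making because a stated rule returns a wrong value and the datum that corrects it is already used in the same section.

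**What to change.** In SAP 4.6.1.1:

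1. Define d in mg as the sum over EX records of days × dose per administration × administrations per day, the last taken from the EX-form dosing frequency. Delete the division by 0.5 from d.
2. Count Cycle 1 Day 1 as one actual dose in d and one planned dose in D, so that a fully adherent child stays at 100%.
3. State that treatment compliance uses the same d.
4. Wording only: make the RDI text use the end date already in the D formula (earliest of last dose above 0 mg, death and data cut-off). State that D is the planned dose per CRF in mg, with the mg/m² sentence as a nominal label.

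The cost is SAP text and derivation code. The frequency is already taken from the EX form for actual duration, so no new or retrospective data collection is needed, and no dose or treatment rule changes.
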